5 SAMPLE SIZE AND POWER

Originally, the sample size was calculated for a comparison test at a 0.05 two-sided significance level, a power of 80%, to detect a difference of 0.05 meters per second (minimal clinically important difference) between active groups and placebo on the change from baseline in the 400 m gait speed at 6 months, with a standard deviation (SD) of 0.13 (estimated from the VIVE2 trial, Fielding et al, 2017^3).

Based on current calculation and given a limited 20% provision for premature withdrawals or lost-to-follow up, a total number of 231 participants will be included in the study.

6 ANALYSIS POPULATIONS

The following analysis populations will be considered.

6.1 Safety population

The safety population consists of all subjects randomized in the study for whom there is any evidence that they used study medication. Subjects are included in the analysis according to the actual treatment received.

The safety population is used for the safety analyses.

6.2 Full Analysis Set (FAS)

The FAS consists of randomized subjects, excluding subjects who failed to take at least one dose of trial medication and had a very early withdrawal (first week after randomization) definitely not related to study medication and lacked any post randomization data (CPMP/ICH/363/96). Subjects are included in the analysis using the FAS according to the treatment to which they were randomized.

6.3 Per-Protocol (PP) population

The PP population consists of all FAS subjects who did not have a major protocol deviation that are related to drug administration (e.g. a long interruption period, as defined in section 7.1 of the protocol) that may have impacted the primary efficacy endpoint. The exclusion of subjects from the PP population will be determined in a blinded data review meeting (BDRM) that will be held prior to the disclosure of the randomization list. Reason(s) for exclusion from the PP population will be provided for each subject. Subjects are included in the analysis using the PP population according to the treatment to which they were randomized.

6.4 Protocol deviations and exclusions from analysis populations

The COVID-19 situation will introduce more protocol deviations than normal. All protocol deviations will be accurately recorded and identified as deviations that incurred due to the COVID-19 outbreak and as reasons why the procedures were not performed according to protocol. They will be assessed and reported in the clinical study report, following ICH E3.

All protocol deviations and exclusions of subjects from analysis populations will be identified at the BDRM prior to full study unblinding, through clinical review and input provided by Biophytis, using the following sources of information:

- Supportive subject listings, ahead of the BDRM, based on data recorded on the eCRF.
- Protocol Deviation Logs,

Deviations from the protocol will be classified as major or minor.

Major protocol deviations to be identified and to be mentioned in the CSR include:

- · Failure to obtain informed consent prior to any study assessment
- Non-compliance with study treatment (<80% treatment compliance or missing compliance) or treatment interruption of > 4 weeks (interruption between two visits or within one visit)
- Failure to perform the 400MWT within 2 week of last dose (14 days or less after last dose)
- Deviation from Inclusion criteria 3, 4, 5, 6, 7
- Deviation from Exclusion criteria 1, 4, 6, 7d, 7e, 7f, 7g, 7h
- Wrong study treatment received (not per randomization list)
- Unintentional unblinding of the investigator and/or subject
- Any other protocol deviation identified as major protocol deviation from above mentioned source of information.

7 STATISTICAL CONSIDERATIONS AND ANALYSIS

7.1 Derived Variables

7.1.1 Derivations for demographic, other baseline characteristics, exposure and compliance

Table 1 provides the list of derived variables for this study.

Variables	Formula	
Demographic and Baseline characteristics		
Body mass index (BMI) (kg/m ²)	weight (kg)/[height (m)]^2	
Derivation of Duration		
Study day at any visit	Date of Interest - Date of first dose of study drug, if date of interest is before date of first dose of study drug	
	If first dose of study treatment is on the same day as Randomisation (Day 0)	
	Date of interest – date of first dose of study drug, if date of interest is on or after date of first dose of study drug.	
	If first dose of study treatment is not on the same day as Randomisation (Day 0)	
	Date of interest – date of first dose of study drug + 1, if date of interest is on or after date of first dose of study drug.	
Extent of Exposure (days)	Date of last treatment intake- Date of first treatment intake + 1	
Extent of Exposure (weeks)	Extent of exposure (days)/7	
Relative day of AE Onset	AE onset date – date of first dose + 1	
Duration of AE	AE end date – AE onset date + 1	
Drug Compliance		
Compliance (%)	$100 \times [(\text{total number of capsules dispensed}) - (\text{total number of capsules returned})] / (total number of capsules planned to be taken per day × duration of study drug exposure in days)$	
Baseline Derivations		
Baseline	The baseline value is defined as the last observation prior to or on the date of the first dose of study drug.	
Change from baseline	Post baseline value – Baseline	

Table 1: List of Derived Variables

Statistical Analysis Plan Protocol Number: BIO101-CL03 Version Final 2.0, Date: 04JUN2021

Page 20 of 69

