5 STUDY POPULATION

231 community dwelling older adults (men or women \geq 65 years) living at home and reporting a loss of physical functions over the last six-twelve months and considered at risk of mobility disability will be included in this randomized, interventional clinical trial, with 64 patients per treatment group and a treatment period of 26 to 39 weeks. 39 additional participants will be randomized to allow a 20% of non-evaluable withdrawals or lost to follow-up for a total of 231 older adults included in the US and the EU.

It is expected, that due to COVID-19 related restrictions, that the number of non-evaluable withdrawals will be higher than 20%. However, reassessment of the sample size, will take place, as a part of the interim analysis, that will take place after restrictions are lifted.

A predefined subgroup efficacy analysis will also be performed in a number of pre-identified, at-

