6.1.2 DOSING AND ADMINISTRATION

Three doses are tested in this study: 175 mg b.i.d. of BIO101, 350 mg b.i.d. of BIO101 or placebo b.i.d. A rationale for the doses selected of the study drug is provided in section 4.3.

Administered daily dose is the same throughout the whole treatment period.

All therapeutic units (175 mg BIO101 b.i.d. or 350 mg BIO101 b.i.d. or placebo b.i.d.) are identical in compliance with the double-blind process.

Study participants are instructed by the investigator or the investigation center staff to start the treatment the day after randomization; e. g. if the participant is randomized on Friday, he/she will start the investigational treatment on Saturday morning.

Each administration is made of two capsules, to be taken by oral route, swallowed with water or fruit juice or other common soft drinks. Capsules should be taken twice a day: once in the morning and once in the evening. Those can be taken with a meal such as breakfast or dinner,

approximately 12 hours apart. If the participant forgets or is not able to take the capsules at the appointed time, he/she should be instructed not to make up for the missed pills; i.e. to not take more capsules later in the day or the day after.

The four capsules to be taken daily is the same across the entire 6-month treatment period.

Important note: Date of each next visit should be calculated back on Day 0 visit (baseline) in order to not exceed the total duration of 26 weeks of treatment.

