6.4 STUDY INTERVENTION COMPLIANCE

During the COVID-19 outbreak, all participants will be asked to send back all used and unused boxes containing the investigational study drug. These returns are carried out based on the same predefined and specific process as the one applied for the shipment from site to participants home. Adherence to the protocol will be assessed by the Investigator staff by counting the full and empty blisters.

A participant study drug log will be completed (to be kept in the source documents) and recorded into the eCRF. An algorithm will automatically calculate the adherence based on visit dates.

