8.7.2 Analysis of primary efficacy endpoint

The 400MW test used to calculate the 400MW gait speed will be performed at Screening, M3, M6/M9 and last assessment on treatment visits. The Screening value will be considered to be the baseline value. If the screening value is missing the baseline value will be considered as missing.

The main analysis of the primary endpoint (change from baseline to month 6 (M6)/month 9 (M9) in 400MW gait speed) will be performed using the FAS.

Change from baseline to M6/M9 in 400WM gait speed will be summarized by treatment group.

The main hypothesis to be tested in this study is the superiority of at least one dose of active versus placebo on the change from baseline in 400m gait speed after 6 months of treatment.

The null hypotheses H_{01} and H_{02} given below will be tested against the alternative hypotheses H_{A1} and H_{A2} respectively:

$$\begin{split} &H_{01}\!\!:\ \mu_1 - \mu_P \!<\! 0.1, \qquad H_{02}\!\!:\ \mu_2 - \mu_P \!<\! 0.1, \\ &H_{A1}\!\!:\ \mu_1 - \mu_P \geqslant 0.1, \qquad H_{A2}\!\!:\ \mu_2 - \mu_P \geqslant 0.1, \end{split}$$

Where μ_1 and μ_2 denote the mean change from baseline in meters per second in the 400MW gait speed at M6/M9 in the 175 mg BIO101 and 350 mg BIO101 groups. With μ_p denoting the mean change from baseline at M6/M9 in the placebo group. A minimum clinically significant benefit is set at 0.1 meter per second in the mean difference between groups (i.e., superiority margin).

A Mixed Effect Model Repeat Measurement (MMRM) model with fixed factors treatment and center and the baseline score and the stratification factor (gender) will produce an estimate of the contrast at M6/M9 in the change from baseline of the 400MW test gait speed between each active arm and the placebo group (section 8.7.1.1) (after adjustment by the Hochberg procedure (Section 8.7.1.6)).

The same MMRM model will be also fitted for the Per-Protocol population to give an estimand of the efficacy of 175mg BIO101 and 350mg BIO101 in the population with a good compliance to the protocol. The FAS is the main population/set of interest.

A by-subject listing of 400MW data will be provided.

Alternative methods to adjudicate missing data for the primary endpoint like the Bayesian Multiple Imputation (MI) methods will also be considered. Chen at al (2017) demonstrated the interest of applying Bayesian MI method to 400MW non-completers in the LIFE study⁹. More detail please refer to section 8.7.6.

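### Compliance is measured only up to the last dose, so the under-80% rule cannot see early stopping and some early stoppers can remain in the Per Protocol set

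*SAP*

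**What the plan says.** SAP 7.1.1, Table 1, defines compliance as capsules dispensed minus capsules returned, divided by capsules planned per day times the "duration of study drug exposure in days". The same table defines exposure as "Date of last treatment intake- Date of first treatment intake + 1".

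SAP 6.4 then makes this a major deviation: "Non-compliance with study treatment (<80% treatment compliance or missing compliance) or treatment interruption of > 4 weeks". It also lists failure to perform the 400MW within 14 days after the last dose, and it leaves room for any other deviation judged major. Under SAP 6.3, FAS participants with major deviations related to drug administration are removed from the Per Protocol set, case by case, at a blinded data review meeting. Neither section names permanent early discontinuation or sets a minimum exposure.

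SAP 8.7.2 gives the purpose of the Per Protocol MMRM: to describe efficacy "in the population with a good compliance to the protocol". It also plans an ANCOVA of the last assessment on treatment in the Per Protocol population.

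Protocol 6.4 describes adherence differently: "An algorithm will automatically calculate the adherence based on visit dates". The SAP's list of changes from the protocol does not mention the difference.

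**The concern.** The denominator closes on the day the participant stops. Permanent discontinuation, the largest form of non-adherence, therefore cannot lower the figure that is meant to screen for good compliance. The 80% rule measures only how regularly capsules were taken while the participant was still taking them.

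What is at stake is the composition of a prespecified supportive analysis. Where no other rule applies, someone who took less than half of the course can be counted among the good compliers. Protocol section 5 expects non-evaluable withdrawals above 20% because of COVID-19, so early leavers are unlikely to be rare. Leaving them to discretion at the review meeting weakens the prespecification of the set.

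**Working it through.** **Inputs**
- Capsules per day: 4 (Protocol 6.1.2: "The four capsules to be taken daily is the same across the entire 6-month treatment period").
- Course length: "a treatment period of 26 to 39 weeks" (Protocol section 5), that is 26 × 7 = 182 days to 39 × 7 = 273 days. At 26 weeks, 4 × 182 = 728 capsules.
- Compliance and exposure formulas: SAP Table 1.
- M3 walk: week 12 ± 1 week (Protocol 1.3), that is day 84, range 77 to 91.
- 400MW timing rule: 14 days or less after the last dose (SAP 6.4).

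The documents give no compliance figure to reproduce.

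**Step 1. Score for a participant who takes every capsule to day d and returns the rest**

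SAP figure = 4d / (4 × d) = 100% for any d. Share of the 26-week course = 4d / 728.

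| Last dose (day) | Capsules taken | SAP Table 1 | Share of 728 | Days to M3 walk on day 84 (range) |
|---|---|---|---|---|
| 28 | 112 | 100% | 15.4% | 56 (49 to 63) |
| 56 | 224 | 100% | 30.8% | 28 (21 to 35) |
| 70 | 280 | 100% | 38.5% | 14 (7 to 21) |
| 84 | 336 | 100% | 46.2% | 0 (−7 to 7) |

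Imperfect use before stopping can also pass. With 90 of 112 capsules taken by day 28, the SAP figure is 90/112 = 80.4%, against 90/728 = 12.4% of the course.

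**Step 2. Whether the other rules catch the early stopper**
- *14-day rule.* Stoppers on day 28 or 56 who next walk at M3 are beyond 14 days and are flagged. So is anyone with no later walk.
- *Interruption over 4 weeks.* It is not stated whether a permanent stop counts as an interruption, so this rule may or may not apply.
- *Missing compliance.* This catches those for whom no capsule count is available.

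**Step 3. Who breaches no explicit listed rule**
- A participant whose end-of-intervention visit is brought forward at withdrawal (allowed by Protocol 1.3), with the 400MW within 14 days of the last dose.
- A participant who stops shortly before or at M3, walks there and then leaves. Counting only walks on or after the last dose, an M3 walk on day 84 admits stops from day 70 to day 84. A walk on day 77 admits stops from day 63.

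**Step 4. Where their data go**

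The MMRM uses M3 and M6/M9. A participant with only an M3 value informs the M6/M9 contrast indirectly, through the within-subject covariance. The last-assessment ANCOVA can take the M3 walk directly. No rule says to which visit an early end-of-intervention walk is assigned, so its entry into the MMRM depends on visit mapping.

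**The case against.** The strongest reply is that compliance is not the only gate. The 14-day rule already catches most of those who quit after a few weeks and have no walk near the last dose. The blinded review can add deviations, with reasons recorded for each participant. FAS is the main population, and Per Protocol is supportive. All of this stands. A reader might infer that anyone who quits early stays in the Per Protocol set, and the documents do not support that.

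A reader might also infer that the compliance table hides early stopping. It does not do so on its own: SAP 8.6.1 bands exposure by arm (1–27, 28–83, 84–146, 147–181 days and longer), and SAP 8.3 reports discontinuations by visit and reason. Showing on-drug adherence beside duration is a legitimate choice.

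Nor does any section prescribe the planned period as the denominator. Protocol 9.4.6 leaves the calculation to the SAP, and Protocol 6.4 refers to visit dates without naming a planned length. The case rests instead on the mismatch between the rule and the purpose stated in SAP 8.7.2.

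A fixed 39-week denominator for extension participants would be a mistake, because Protocol 1.3 lets their end visit be brought forward. A fully adherent participant finishing at day 217 would score 217/273 = 79.5% and fail.

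One gap remains after all this: a walk close to a permanent stop satisfies every explicit rule, and nothing says that the meeting must exclude that participant.

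**Conclusion.** The point holds in this limited form. The under-80% rule cannot detect permanent early discontinuation, and an identifiable group (a 400MW within 14 days of stopping, followed by leaving) can score up to 100% and remain in the Per Protocol MMRM and last-assessment ANCOVA. For a stop between day 63 and day 84 with every capsule taken, the true share of a 26-week course is 252/728 = 34.6% to 46.2%. With an earlier end-of-intervention visit it is lower.

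The conclusion assumes that unused capsules are returned and counted, that a permanent stop is not treated as an interruption, and that the review meeting adds no exclusion of its own. The documents do not allow a count of affected participants or the size or direction of any effect on the Per Protocol estimate. The FAS analysis is untouched. This should be corrected, but it does not threaten the primary conclusion.

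**What to change.** 1. In SAP Table 1, keep the present ratio and label it adherence while on treatment.
2. Add a second measure for the Per Protocol rule: capsules used / (4 × the larger of 182 days and actual exposure days). A stop on day 84 then scores 336/728 = 46.2%. A fully adherent extension participant ending at day 217 scores 868/868 = 100%. For anyone exposed for 182 days or more, the result equals the current one. With perfect daily use, passing takes 146 days (0.8 × 182 = 145.6).
3. State in SAP 6.3 and 6.4 that permanent discontinuation giving under 80% on this measure is a major deviation related to drug administration.
4. Reconcile the formula with the visit-date basis in Protocol 6.4, or record the departure in the SAP's list of changes.

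The change uses dispensing, return and intake data already collected. The cost is a few lines of SAP text and a somewhat smaller Per Protocol set. A few borderline cases will move: a participant who finishes at day 175, the early edge of the M6 window, would need 145.6/175 = 83.2% on-treatment adherence to pass, where 80% suffices now.

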7.1.2 Derivations for efficacy endpoints

7.1.2.1 PF-10 sub-score from the SF-36

SF-36⁵ (version 2) Quality of Life questionnaire was developed as a general measure of perceived health status. It comprises 36 items, allowing the calculations of eight sub-scores: Physical Functioning (10 items), Role limitations due to-physical problems (4 items), Bodily Pain (2 items), General Health perceptions (5 items), Vitality (4 items), Mental Health (5 items), Role-limitations due to emotional problems (3 items) and Social Functioning (2 items). Two summary scores of health-related quality of life are also calculated; physical component summary (PCS) and the mental component summary (MCS).

SF-36 (version 2) data are recorded at baseline, M3, M6/M9 or end-of-intervention visits.

The method for calculating the SF-36 sub-scores, including PF-10 is shown in the Appendix B - Short Physical Performance Battery (SPPB)

Summary performance score: Each of the three performance measured is assigned a score ranging from 0 to 4, with 4 indicating the highest level of performance and 0 the inability to complete the test. For the test of balance, participants are assigned a score of 1 if they can hold a side-by-side standing position for 10 seconds but are unable to hold a semi-tandem position for 10 seconds; a score of 2 is assigned if they can hold a semi-tandem position for 10 seconds; a full-tandem position for 3 seconds; a score of 3 is assigned if they can stand in a full-tandem position for 3 seconds; a score of 4 is assigned if they can stand in a full tandem position for 10 seconds.

Four categories are computed for walking speed and chair stands, according to cut-off points that are based on quartiles of the time to perform each task assessed in the EPESE. The time of the faster of two walks is scored as follows: > 8.7 sec = 1; 6.21 to 8.70 sec = 2; 4.82 to 6.20 sec = 3; < 4.82 sec = 4; a score of 0 is assigned to participants unable to perform the test. The time required to perform five chair stands is scored as follows: $\ge 16.70 \text{ sec} = 1$; 13.70 to 16.69 sec = 2; 11.20 to 13.69 sec = 3; $\le 11.19 = 4$. A score of 0 is assigned to participants unable to perform the task. A summary score ranging from 0 (worst performers) to 12 (best performers) is calculated by adding subscores from the walking speed, chair stands and balance tests.

Appendix C

Details of how to deal with missing data are also mentioned.

Standardized sub-scale scores will be presented to one decimal place. Handling of missing data and outliers.

Missing data will not be imputed in the primary analysis of the primary efficacy endpoint. No imputation for missing data will be used for the descriptive statistics and listings. Imputation for missing SF-36 sub-scale score data is detailed in Appendix B - Short Physical Performance Battery (SPPB)

Summary performance score: Each of the three performance measured is assigned a score ranging from 0 to 4, with 4 indicating the highest level of performance and 0 the inability to complete the test. For the test of balance, participants are assigned a score of 1 if they can hold a side-by-side standing position for 10 seconds but are unable to hold a semi-tandem position for 10 seconds; a score of 2 is assigned if they can hold a semi-tandem position for 10 seconds; a full-tandem position for 3 seconds; a score of 3 is assigned if they can stand in a full-tandem position for 3 seconds; a score of 4 is assigned if they can stand in a full tandem position for 10 seconds.

Four categories are computed for walking speed and chair stands, according to cut-off points that are based on quartiles of the time to perform each task assessed in the EPESE. The time of the faster of two walks is scored as follows: > 8.7 sec = 1; 6.21 to 8.70 sec = 2; 4.82 to 6.20 sec = 3; < 4.82 sec = 4; a score of 0 is assigned to participants unable to perform the test. The time required to perform five chair stands is scored as follows: $\ge 16.70 \text{ sec} = 1$; 13.70 to 16.69 sec = 2; 11.20 to 13.69 sec = 3; $\le 11.19 = 4$. A score of 0 is assigned to participants unable to perform the task. A summary score ranging from 0 (worst performers) to 12 (best performers) is calculated by adding subscores from the walking speed, chair stands and balance tests.

Appendix C.

7.1.3 Missing data analysis methods for sensitivity analyses

Alternative methods to adjudicate missing data for the primary endpoint like the Bayesian Multiple Imputation (MI) methods could be considered and adopted before unblinding and preparation of the final analysis. This would be documented in a SAP amendment.

7.1.4 Handling of missing or incomplete dates

Imputation rules for missing or partial AE start date are defined below:

If only Day of AE start date is missing:

If the AE start year and month are the same as that for the first dose date, then:

- If the full (or partial) AE end date is NOT before the first dose date or AE end date is missing, then impute the AE start day as the day of first dose date;
- Otherwise, impute the AE start day as 1.

If Day and Month of AE start date are missing:

If AE start year = first dose year, then:

- If the full (or partial) AE end date is NOT before the first dose date or AE end date is missing, then impute the AE start month and day as the month and day of first dose date;
- Otherwise, impute the AE start month as January and the day as 1.

If Year of AE start date is missing:

If the year of AE start is missing or AE start date is completely missing then this will be queried, with no imputation. Also compare the full (or partial) AE end date to the first dose date. If the AE end date is before the first dose date then the AE should be considered as a pre-treatment AE. Otherwise, the AE will be considered as TEAE.

Imputation rules for missing or partial medication start/stop dates are defined below:

Missing or partial medication start date:

- If only day is missing, use the first day of the month.
- If day and month are both missing, use the first day of the year.
- If day, month and year are all missing, use first dose date -1.

Missing or partial medication stop date:

- If only day is missing, use the last day of the month.
- If day and month are both missing, use the last day of the year.
- If day, month and year are all missing, assign 'continuing' status to stop date

